### 6.1 Classification Of Adverse Events By Severity & Relationship To Study Drug Administration

#### 6.1.1 Adverse Event

Any unfavorable and unintended sign (including an abnormal laboratory finding), symptom or disease temporally associated with the use of a medical treatment or procedure regardless of whether it is considered related to the medical treatment or procedure (attribution of unrelated, unlikely, possible, probable, or definite).

#### 6.1.2 Life-Threatening Adverse Event

Any adverse event that places the patient or subject, in view of the investigator, at immediate risk of death from the reaction.

#### 6.1.3 Serious Adverse Event (SAE)

Any adverse event occurring at any dose that results in any of the following outcomes: Death, a life-threatening adverse event, inpatient hospitalization or prolongation of existing hospitalization, a persistent or significant disability/incapacity, or a congenital anomaly/birth defect.

Please note for **hospitalization** – All hospitalizations (or prolongation of existing hospitalization) for medical events equivalent to CTCAE Grade 3, 4, 5 must be reported regardless of the requirements for Phase of study, expected or unexpected, and attribution. For example, do not report an admission for pharmacokinetic sampling, but do report an admission for a myocardial infarction.

#### 6.1.4 Toxicity

Toxicity is a term NOT clearly defined by regulatory organizations. Toxicity has been described as an adverse event that has an attribution

of possibly, probably or definitely related to investigational treatment. To minimize confusion the NCI would recommend that the term toxicity NOT be utilized for adverse event reporting purposes. The CTCAE continues to use the term 'toxicity' because of familiarity.

#### 6.1.5 Unexpected Adverse Event

Any adverse event that is not listed in the NCI Agent Specific Expected Adverse Event List. This list is updated electronically in real time.

#### 6.1.6 Adverse Event Expedited Reporting System (AdEERS) (formerly known as Adverse Drug Reaction Reporting).

An electronic system for expedited submission of adverse event reports.

#### 6.1.7 Attribution

The determination of whether an adverse event is related to a medical treatment or procedure. Attribution categories:

Definite – The AE *is clearly related* to the investigational agent(s).

Probable – The AE *is likely related* to the investigational agent(s).

Possible – The AE *may be related* to the investigational agent(s).

Unlikely – The AE *is doubtfully related* to the investigational agent(s).

Unrelated – The AE *is clearly NOT related* to the investigational agent(s).

## 6.2 Adverse Event Reporting To Novartis

Novartis will need to be notified within 24 hours of any SAE regardless of the presumed relationship to Gleevec.

Instructions for rapid notification of SAEs.

### 6.2.1 Reporting Responsibility

Each SAE (but not pregnancies) must be reported by the Investigator to Novartis within 24 hours of learning of its occurrence, even if it is not felt to be treatment-related. Follow-up information about a previously reported SAE must also be reported to Novartis within 24 hours of receiving it. If the SAE has not been previously documented (new occurrence) and it is thought to be related to study drug (or therapy), the Medical Safety Expert of the Clinical Safety & Epidemiology (CS&E) Department may contact the Investigator to

obtain further information. If warranted, an investigator alert may be issued, to inform all investigators involved in any study with the same drug (or therapy) that this SAE has been reported.

### 6.2.2 Reporting Procedures

The Investigator must complete the FDA MedWatch 3500 form and Novartis SAE coversheet (see Appendix XVII) in English, assess the relationship to study treatment and send the initial completed MedWatch form and Novartis SAE coversheet by [contact] within 24 hours to the local Novartis Clinical Safety & Epidemiology (CS&E) Department. The Investigator must then ensure that the form and coversheet are accurately and **fully** completed with follow-up information and fax those to Novartis CS&E Department within 2 to 3 calendar days for deaths or life-threatening events and 5 calendar days for other SAEs. The original and the duplicate copies of the FDA MedWatch form, Novartis SAE coversheet, and the fax confirmation sheet must be kept with the CRFs at the study site.

Follow-up information should describe whether the event has resolved or continues, if and how it was treated, and whether the patient continued or discontinued study participation. The MedWatch form, Novartis SAE coversheet, and fax confirmation sheet must be retained. Pregnancy follow-up should describe the outcome of the pregnancy, including any voluntary or spontaneous termination, details of the birth, and the presence or absence of any congenital abnormalities or birth defects.

## 6.3 Adverse Events With Commercial Agents

The AE should be reported on the FDA Form 3500 MedWatch (available from the FDA website at [www.fda.gov/medwatch](http://www.fda.gov/medwatch)). The following AEs should be reported:

- All life-threatening events (Grade 4), which may be due to drug administration.
- All fatal events (Grade 5) while on study (or within 30 days of treatment)
- First occurrence of any previously unknown clinical event (regardless of Grade).

The completed form should be forwarded to:

AMC Operations Center  
The EMMES Corporation  
[name]  
[name]  
[contact]

All AEs, regardless of severity, and whether or not ascribed to study drug administration, will be recorded in the appropriate section of the CRF. Patients withdrawn from the study due to AEs will be followed by the Investigator until the outcome is determined and, when appropriate, additional written reports and documentation will be provided.

## **7.0 CRITERIA FOR TREATMENT DISCONTINUATION**

- Study medication will be interrupted or permanently discontinued for treatment related toxicities as outlined in Sections 5.4-5.6.
- Disease progression.
- Subjects who become pregnant or breast-feed or who require systemic chemotherapy for the treatment of a malignancy other than KS.
- Subjects who require treatment with medications disallowed as outlined in Sections 5.6.1.4–5.6.1.7.
- Subjects who are noncompliant with respect to taking drugs, keeping appointments or having tests required for the evaluation of drug safety and efficacy.
- Subjects have the right to withdraw from the study at any time for any reason.
- The Investigator has the right to remove subjects from the study for clinical reasons which he/she believes are life-threatening to the subject even if such reasons do not fall into the toxicity classifications discussed above.

## **8.0 POST-TREATMENT EVALUATION AND EVALUATION AT EARLY DISCONTINUATION OF THERAPY**

Thirty days after discontinuation, a follow-up visit will include: **a complete physical exam including: vitals signs, weight, tumor assessment, Karnofsky performance status (Appendix IV), and toxicity evaluation.**

- At a subject's final study visit, the off-study form will be completed. Permanent discontinuation of drug will be documented.
- Subjects who withdraw for toxicity reasons should be followed until the toxicity resolves/returns to baseline, or at least 1 month, whichever is later. In addition, subjects who go off study for reasons other than toxicity should be followed for at least 1 month after discontinuing drug.

## 9.0 EVALUATION OF RESPONSE

### 9.1 Definition of Response

- 9.1.1 Complete response (CR) is defined as the absence of any detectable residual disease, including tumor-associated edema, persisting for at least 4 weeks. In patients whose pigmented (brown or tan) macular skin lesions persist after apparent CR, biopsy of at least one representative lesion is required in order to document the absence of malignant cells. In patients known to have had visceral disease, an assessment at restaging with appropriate endoscopic or radiographic procedures should be made.
- 9.1.2 Clinical CR is defined as the absence of any detectable residual disease, including tumor-associated edema, persisting for at least 4 weeks; AND
- For patients with pigmented (brown or tan) macular skin lesions persisting after apparent CR, biopsy of a representative lesion documenting the absence of KS cells is not required; AND
  - For patients known to have had visceral disease, restaging with appropriate endoscopic or radiographic procedures is contraindicated or otherwise not performed.
- 9.1.3 Partial Response (PR) is defined as no new lesions (skin or oral), or no new visceral sites of involvement (or the appearance or worsening of tumor-associated edema or effusions); AND
- A 50% or greater decrease in the number of all previously existing lesions lasting for at least 4 weeks; OR
  - Complete flattening of at least 50% of all previously raised lesions (i.e., 50% of all previously nodular or plaque-like lesion become macules); OR
  - A 50% decrease in the sum of the products of the largest perpendicular diameters of the marker lesions.
- NOTE – Patients with residual tumor-associated edema or effusion who otherwise meet the criteria for CR will be classified as having a PR.
- 9.1.4 Stable disease is defined as any response not meeting the criteria for CR, PR, or progressive disease.
- 9.1.5 Progressive disease is defined as follows:
- For patients with <50 cutaneous lesions  $\geq 25\%$  increase in the sum of perpendicular diameters of the indicator lesions.

- OR  $\geq$  25% increase in the total lesion count, or a minimum of 5 new lesions, whichever is greater,
- OR  $\geq$  25% increase in the number of raised lesions (minimum of 5 new raised lesions if there are very few raised lesions, for example  $\leq$  8), whichever is greater.

Note: There are body sites where disease is particularly difficult to evaluate, and a few new lesions may be counted in spite of the fact that a patient is not actually progressing. For example, lesions of the foot, particularly those which are flat, are difficult to evaluate because their intensity may be variable based on how much edema is present, how much the person walked the day before, how long their feet have been in a dependent position prior to the physical exam, etc.

- For patients with  $\geq$ 50 cutaneous lesions:
  - $\geq$  25% increase in the sum of the perpendicular diameters of the indicator lesions.
  - OR  $\geq$  25% increase in the total number of lesions in the prospectively defined anatomic sites containing representative numbers of lesions,
  - OR a total of 5 new lesions in anatomic sites which were previously documented as having no evidence of cutaneous disease on the whole body diagram,
  - OR (25% increase in the number of raised lesions. Photographic documentation of “gross” or significant progression, particularly in areas that were not being followed, will be of particular value.

In order to classify a response as PR, the patient must have at least a PR in the cutaneous or noncutaneous sites of disease, and no evidence of progression as defined in the above criteria. In order to classify a response as a CR, the patient must have a CR in both the cutaneous (if applicable) and noncutaneous (if applicable) sites of disease and no evidence of progression as defined by the above criteria.

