#### Noncutaneous Progression

Progressive disease includes new visceral sites of involvement or progression of visceral disease or the development of new or increasing tumor-associated edema or effusion lasting at least 1 week, which interferes with the patient’s normal activities. Progressive visceral disease, for measurable and evaluable disease, should be based on RECIST criteria.

- 9.1.6 Recurrent disease is defined as the appearance of tumor following documentation of a complete remission.
- 9.1.7 Time to response is defined as time from the first dose of Gleevec until documentation of first response.
- 9.1.8 Time to progression is defined as time from initiation of Gleevec to documentation of first progression.
- 9.1.9 Response duration is defined as the time from first documentation of response to documentation of first progression.

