## 12.0 STATISTICAL CONSIDERATIONS

### 12.1 Sample Size Estimation

The response rate (CR + PR) to imatinib in the pilot study is 50% to date. It is well known that some patients have regression of their KS after beginning HAART therapy. In order to minimize the effect of HAART being a potential confounding factor in response rates, recent studies have required patients on HAART to be on stable regimens for 12 weeks prior to initiation of treatment. Recent results from two placebo-controlled studies suggest as many 20% of responses in KS clinical trials may be delayed responses to HAART alone.[19, Walmsley, 1999 #136] Simon's two-stage design will be used to test the null hypothesis that the response rate (CR + PR) is 20% against the alternative that it is 50% at the one-sided 0.05 significance level with power of 0.90. Ten patients will be enrolled in the first stage. If no more than two patients respond, then the study will be stopped. If at least three patients respond, then the study will enroll up to a total of 22 patients. If no more than seven patients respond, the drug will be considered ineffective. If at least eight patients respond, the null hypothesis will be rejected in favor of the alternative hypothesis. The probability of early termination of the study is 0.68.

In our original estimate, we assumed a drop out rate of 10-15% based on our experience in the pilot study and calculated a sample size of 25 patients. However, we have had a higher drop out rate. Consequently, based on a drop out rate of 20-30%, we plan to roll a total of 30 patients to have 22 patients evaluable for response.

In the pilot study, we found that decreasing the dose of imatinib by 33% (600 mg/day to 400 mg/day) dramatically decreased the incidence of AEs. This dose reduction should reduce the steady state concentration of imatinib and its metabolite by 1 standard deviation of steady state plasma concentration, assuming constant clearance. This observation suggests a change in the plasma concentration imatinib and/or its metabolite of 1 standard deviation would be significant in our patient population. Based on this assumption, a PK sampling of 12 patients will provide a power of 88% to detect a 1 standard deviation change in the steady state level of imatinib and its metabolite with a type I error of 0.05 using a two-sided paired t-test.

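### Of the three listed partial-response routes in Section 9.1.3, only lesion count must last 4 weeks; flattening and marker-lesion area state no duration, so one assessment can count toward the primary CR + PR rate.

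*Combined protocol and SAP*

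**What the plan says.** Section 9.1.3 opens with conditions that apply to every PR: "no new lesions (skin or oral), or no new visceral sites of involvement (or the appearance or worsening of tumor-associated edema or effusions"). Three routes follow, joined by OR:

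- Lesion count: "A 50% or greater decrease in the number of all previously existing lesions lasting for at least 4 weeks".
- Flattening: "Complete flattening of at least 50% of all previously raised lesions".
- Marker-lesion area: "A 50% decrease in the sum of the products of the largest perpendicular diameters of the marker lesions".

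The 4-week phrase stands inside the first route only. A note to 9.1.3 adds a further path: a patient who meets CR except for residual edema or effusion is a PR.

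CR (9.1.1) and clinical CR (9.1.2) both require "absence of any detectable residual disease, including tumor-associated edema, persisting for at least 4 weeks". The classification rule at the end of 9.1.5 asks for a PR in cutaneous or noncutaneous sites with "no evidence of progression as defined in the above criteria". Section 9.1.7 runs time to response up to the first documented response. Section 9.1.9 reads: "Response duration is defined as the time from first documentation of response to documentation of first progression".

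Section 12.1 tests CR + PR, 20% against 50%, in a Simon two-stage design. The trial continues with at least 3 responses in 10 and rejects the null with at least 8 in 22.

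**The concern.** The primary endpoint is a count of responders, and the rule for joining that count differs by route. A patient whose lesion number halves must hold the reduction for 4 weeks. A patient whose marker area halves at a single visit, or half of whose raised lesions flatten at a single visit, qualifies at once. The documents give no reason for the difference.

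Two careful readers could also score the same patient differently, one carrying the 4 weeks across all three routes and the other not. In an open-label, single-arm trial with skin measurements, an ambiguous responder rule is undesirable, and both decision rules turn on single patients: 2 of 10 stops where 3 of 10 continues, and 7 of 22 fails where 8 of 22 rejects.

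**Working it through.** **Step 1. Does any other section supply the missing duration?**

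| Place | What it adds on duration |
|---|---|
| 9.1.1, 9.1.2 (CR, clinical CR) | 4 weeks |
| 9.1.3, lesion count | 4 weeks |
| 9.1.3, flattening | none |
| 9.1.3, marker-lesion area | none |
| 9.1.3, note on residual edema or effusion | 4 weeks, inherited from CR |
| End of 9.1.5 (overall PR) | none; no progression required |
| 9.1.7, 9.1.9 | none; both use first documentation |
| 4.2.1.1 and Appendix I | assessment dates; no confirming assessment named |
| 12.1, 12.2 | none; CR + PR used without a confirmation rule |

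Nothing supplies it. The rule at the end of 9.1.5 also allows PR in noncutaneous sites, for which 9.1.3 gives no separate criterion or duration.

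**Step 2. Direction.** Every patient who qualifies under a 4-week rule on all routes also qualifies under the current text. The current count is therefore equal or higher, never lower.

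**Step 3. Reproduce the design.** Inputs from 12.1: 10 patients in stage 1, continue with 3 or more; 22 in total, reject with 8 or more. With X binomial(10, p) and Y binomial(12, p),

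P(reject) = Σ over x = 3 to 10 of P(X = x) × P(Y ≥ 8 − x).

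At p = 0.20 the terms are 0.01461 (x = 3), 0.01809 (x = 4), 0.01167 (x = 5), 0.00399 (x = 6), 0.00073 (x = 7) and 0.00008 (x ≥ 8), which sum to 0.0492. P(X ≤ 2) = 0.678. At p = 0.50, P(reject) = 0.9022. These agree with the stated 0.05, 0.68 and 0.90.

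**Step 4. Sensitivity to one response.** A rejection is reversed by reclassifying one response if the total is exactly 8, or if stage 1 has exactly 3 responses (one of which is reclassified) and the total is 9 or more.

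| True rate | Total exactly 8 | Stage 1 exactly 3, total ≥ 9 | Sum | Share of rejections |
|---|---|---|---|---|
| 20% | 0.0304 | 0.2013 × 0.0194 = 0.0039 | 0.0343 | 0.0343 / 0.0492 = 70% |
| 50% | 0.0643 | 0.1172 × 0.6128 = 0.0718 | 0.1361 | 0.1361 / 0.9022 = 15% |

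These shares show how often the conclusion hangs on one response. They do not show how often a response would fail to last.

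**Step 5. Type I error, by assumption only.** Suppose the 20% null described 4-week responses and single-visit responses raised the counted null rate. P(reject) would be 0.089 at 22.5%, 0.10 at 23.1%, 0.143 at 25% and 0.296 at 30%. None of these rates is in the documents. If the 20% already reflects the current wording, the figure stays at 0.049.

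**Step 6. Power if the confirmed rate is below 50%.** The same formula gives 0.9022 at 50%, 0.8065 at 45% and 0.6630 at 40%. The 40% case corresponds to one of the pilot's five responders in ten (Section 1.1.5) not being confirmed: 4/10.

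**Step 7. Can the schedule confirm a response?** Section 4.2.1.1 assesses tumor on Day 29, Day 56 and every 2 months thereafter. Day 29 to Day 56 is 56 − 29 = 27 days, one short of 4 weeks. The 7-day window on each visit allows 49 − 36 = 13 to 63 − 22 = 41 days.

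**The case against.** **The phrase was probably meant for all routes.** With CR and clinical CR both at 4 weeks, misplaced wording is plausible, and the stem of 9.1.3 is itself loosely drafted: its conditions are joined by *or*, though they are read here as all required. This stands. A reader should not infer a deliberate choice to accept unconfirmed PRs. But the text does not say 4 weeks for all routes, so it still needs correcting.

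**Lesion count is not the only sustained path to PR.** Correct. The residual-edema note inherits the 4 weeks from CR. The gap concerns flattening, marker area and noncutaneous PR.

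**No harm is shown.** A reader might infer that type I error exceeds 0.05. The documents do not support that, because the definition behind the 20% is not given and no transient-response rate is available. Sensitivity to one response is also common to any threshold design. What remains is an inconsistent rule on the primary endpoint.

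**The remedy may fit the 50% alternative less well than the present wording does.** Section 1.1.5 reports the pilot responses after 4 weeks of therapy and does not say that they were sustained. This stands, and power must be restated.

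**A sensitivity analysis would be lighter than amending an accruing trial.** It would show the difference between the rules but leave the decision rule open to two readings.

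**Conclusion.** The point holds as an inconsistency in the primary endpoint that should be corrected. Followed literally, the CR + PR count mixes responses that lasted 4 weeks with responses that may have been seen once, according to route. A single-visit PR is not unconditional: it still requires no new lesions or visceral sites, no new or worse edema or effusion, and no progression.

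The direction is certain (equal or higher count than under a uniform rule), but the size is not derivable. The sample size, cut-offs and stated error rates in 12.1 are arithmetically correct and are not in question. The conclusion rests on reading the bullets of 9.1.3 as printed and on the absence of a duration elsewhere in the documents.

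**What to change.** - **Wording.** End the stem of 9.1.3 with a requirement that at least one of the listed criteria be met and maintained for 4 weeks or longer, and delete the phrase from the lesion-count route. State that the same duration applies to PR in noncutaneous sites.
- **Confirmation.** Name the assessment that confirms a response and the day tolerance accepted, given the 27-day nominal gap between Day 29 and Day 56. Say whether the tumor assessments at discontinuation (4.3.5) and 30 days afterwards (8.0) count. Keep the first of the two assessments as the response date for 9.1.7 and 9.1.9.
- **Application.** Section 12.1 reports the drop-out seen so far, so accrual has begun. Make the change without reference to observed responses and apply it to every patient, including those off study and any stage 1 count. State beforehand what follows if a stage 1 count already taken falls below three.
- **Reporting.** Give the response rate under the 4-week rule and, as supportive, under the current wording.
- **Power.** Keep 22 patients and the cut-offs, but state in 12.1 that the 50% comes from a pilot read at 4 weeks and not shown to be sustained, with power 0.90, 0.81 and 0.66 at confirmed rates of 50%, 45% and 40%.

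**Cost.** The text change is short, but it amends the primary endpoint of an open trial, requires patients already assessed to be re-read and may reduce power. Some responses first seen late on treatment could not be confirmed, or would need another visit, if off-treatment assessments are excluded. How many cannot be judged from the documents: the pilot's median treatment duration was 7 weeks, non-responders included, and 12.1 now plans for 20-30% drop-out.

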#### Noncutaneous Progression

Progressive disease includes new visceral sites of involvement or progression of visceral disease or the development of new or increasing tumor-associated edema or effusion lasting at least 1 week, which interferes with the patient’s normal activities. Progressive visceral disease, for measurable and evaluable disease, should be based on RECIST criteria.

- 9.1.6 Recurrent disease is defined as the appearance of tumor following documentation of a complete remission.
- 9.1.7 Time to response is defined as time from the first dose of Gleevec until documentation of first response.
- 9.1.8 Time to progression is defined as time from initiation of Gleevec to documentation of first progression.
- 9.1.9 Response duration is defined as the time from first documentation of response to documentation of first progression.

